**Aim 10**

The secondary outcome measure of adjustable socket mode preference was taken after testing the socket in all test modes. A Shapiro-Wilk test will be used to determine normalcy. Normally distributed will be compared using paired t-tests. If data is not normally distributed, a Wilcoxon Signed Rank test will be used to make comparisons. A significance level of 0.05 will be used to determine whether socket preference was statistically significant following testing the socket in all modes.

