### **SPECIFIC AIMS:**

Aim 2: Assess the performance of an adjustable socket in our laboratory.

Aim 3: Assess how prosthetic users use a wireless, adjustable socket to manage change in limb volume.

Aim 4: Assess the performance of an automatic, adjustable socket in our laboratory.

Aim 6A: Assess the performance of an adjustable socket in our laboratory that is able to quickly enlarge and quickly return to normal size to enable full or partial doffing while seated.

Aim 6B: Assess how prosthetic users respond to an adjustable socket that is able to quickly enlarge and quickly return to normal size automatically to enable full or partial doffing while seated.

Aim 8: Assess how prosthetic users respond to an adjustable socket, which is attached to their liner, that is able to enlarge while seated and return to normal size before ambulation.

Aim 9: Assess how prosthetic users respond to an adjustable socket, which is attached to their liner, that is able to quickly enlarge and quickly return to normal size automatically during ambulation.

Aim 10: Involves in-field testing of the adjustable prosthetic system developed in the prior aims. Subjects will use the test socket in 3 different configurations throughout the course of this study: (A) automatic control mode, (B) manual control mode, and (C) adjustment disabled mode. (A) In the automatic control mode, sensors that are built into the socket will be used to monitor the movement and position of the limb within the socket and use this information to automatically adjust the socket panels in an effort to improve the fit. Adjustments may occur while they are sitting, standing, and walking. The system will be integrated into an app on a smartphone. We will provide the phone. (B) In the manual control mode subjects will be able to make adjustments to the panels using the smartphone app. Changes will not be made automatically. (C) In the disabled mode, the ability to adjust panels will be turned off.

A description of the study procedures that will be used is given here; the attached table outlines what specific procedures will be done at the study visits for each aim:

|  | Aim 2, Aim 8,
Aim 9   | Aim 3  | Aim 4  | Aim 6A  | Aim 6B   |
|--|--|--|--|---|--|

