| Lab Visit 2—up to 3 weeks after visit 1, when their adjustable test socket is ready                              | 3 hours
-Test socket fit
-May place sensors onto socket and/or liner to measure activity and limb movements in the socket
-Teach participant how to use the adjustable socket in the 3 different modes that will be tested. Once they are comfortable, they will leave the lab for 4-7 days with socket in the first mode to be tested. |
| Research engineer visits (2) –at the end of each of the first two socket test modes                              | 1-2 hours each.
-Questionnaire and dialog regarding socket test mode that was just completed
-Socket will be changed over to next test mode
-Refresh participant training on how to use the new test mode
-Once comfortable in new test mode, subject will continue using the mode for next 4-7 days.                                |
| Lab Visit 3—at the end of the 3 rd socket test mode   | 1-3 hours
-Questionnaire and dialog regarding socket test mode that was just completed AND all socket modes tested in the study
-Original socket will be returned to initial state and all study instruments will be retained by the lab   |

Primary quantitative data will be collected via custom study instruments, such as a bioimpedance measurement system to assess limb volume changes and inductive sensors built into the test socket wall to measure limb movement/distance. Qualitative data will be collected from participants directly through self-report of their health history, during study procedures. All data for this research will be collected prospectively.

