**Aim 3**

The primary outcome measure of change in limb movement was taken at times of socket enlargement and socket reduction. A Shapiro-Wilk test will be used to determine normalcy. Normally distributed data will be compared using paired t-tests. If data is not normally distributed, a Wilcoxon Signed Rank Test will be used to make comparisons. A significance level of 0.05 will be used to determine whether measured differences in limb movement were statistically significant between socket enlargement and socket reduction.

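### Aim 10 analyses preference among three socket modes with two-condition tests, and states no contrast, no three-mode rule and no response format

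*Combined protocol and SAP*

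**What the plan says.** Under Specific Aims, Aim 10 is a field comparison within participants: "Subjects will use the test socket in 3 different configurations throughout the course of this study". The three are automatic control, manual control and adjustment disabled. The Aim 10 visit table has each mode used for 4-7 days in turn. Research engineer visits with a questionnaire take place "at the end of each of the first two socket test modes". Lab Visit 3 then includes "Questionnaire and dialog regarding socket test mode that was just completed AND all socket modes tested in the study".

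The Aim 10 section of the Statistical Analysis Plan gives an analysis for one outcome only: "The secondary outcome measure of adjustable socket mode preference was taken after testing the socket in all test modes". After a Shapiro-Wilk test, the rule is "Normally distributed will be compared using paired t-tests" and "If data is not normally distributed, a Wilcoxon Signed Rank test will be used to make comparisons". It ends: "A significance level of 0.05 will be used to determine whether socket preference was statistically significant following testing the socket in all modes".

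Neither document part says which modes are compared, gives an overall test across the three, sets a testing order or adjustment, or describes the preference item (a score for each mode, a ranking, or one chosen mode).

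**The concern.** A paired t-test or signed-rank test answers a question about two conditions, whereas the closing sentence of the Aim 10 section asks about all modes together. To get from one to the other, the analyst must decide which pair or pairs to test, and how to treat several results if there are several. The plan makes neither decision. The Aim 3 section uses the same template, but its significance sentence names the two conditions: "statistically significant between socket enlargement and socket reduction". Aim 10 has no such clause, and it has three conditions.

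The undefined response adds to this. With a numeric value per mode, a paired test is sound for one stated contrast. With a single chosen mode the data are nominal: there is no distribution for Shapiro-Wilk to assess, and no natural paired difference to test.

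At stake is a statement that users prefer one mode in the field. As written, that statement could rest on a contrast picked after the data are seen.

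**Working it through.** **Inputs from the documents.** Three modes (Specific Aims, Aim 10); every participant uses all three (Aim 10 visit table); paired t or signed-rank after Shapiro-Wilk, at 0.05 (SAP, Aim 10). The 0.05 is an input, and the plan gives no derived figure for Aim 10, so there is nothing to reproduce.

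**Assumptions, because the documents are silent.** n = 8 to 30; two-sided tests; for the inflation figures, all three pairs tested without adjustment. All error rates are under equal preference.

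**Step 1: bounds.** Three modes give 3 × 2 / 2 = 3 pairs. The upper bound on the chance of at least one false positive is 3 × 0.05 = 0.15. If the tests were independent it would be 1 − 0.95³ = 0.1426. They are not independent, since (A − B) + (B − C) = A − C, so the dependence has to be simulated or enumerated.

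**Step 2: a value per mode.** Normal scores with correlation 0.5, used as they are, rounded to 1-5, or turned into ranks. For each pair: Shapiro-Wilk on the differences, then paired t if p ≥ 0.05, otherwise signed-rank. Chance of any p < 0.05 among the three pairs, 6,000 simulations:

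| Response (signed-rank version) | n=8 | n=12 | n=20 | n=30 |
|---|---|---|---|---|
| Continuous, approximate | 13.1% | 12.8% | 12.3% | 12.0% |
| Continuous, exact | 12.9% | 12.7% | 12.3% | 12.0% |
| Ratings 1-5, approximate | 11.5% | 12.1% | 11.7% | 12.2% |
| Ratings 1-5, exact | 7.3% | 9.7% | 8.5% | 10.2% |
| Ranks, approximate | 12.7% | 12.0% | 12.0% | 11.8% |
| Ranks, exact | 6.4% | 9.2% | 11.5% | 10.1% |

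The simulation error near 12% is √(0.12 × 0.88 / 6000) = 0.4 points. A repeat with 10,000 simulations gave 11.4%-13.1% for the approximate test, and a separate run of 4,000 for continuous scores gave 12.4%-13.5%. Hence about 11%-14% with the approximate test, and less with the exact test on coarse data.

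**Step 3: a single choice.** To apply the planned tests at all, each mode must be coded 1 if chosen and 0 if not, and the codes differenced. The plan does not describe this coding; it is used here only to see what the rule would do. Full enumeration of the 3ⁿ outcomes:

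| Procedure | n=8 | n=10 | n=12 | n=20 | n=30 |
|---|---|---|---|---|---|
| Three pairs, approximate | 11.66% | 9.31% | 9.84% | 10.21% | 12.71% |
| Three pairs, exact | 3.34% | 4.37% | 5.37% | 6.23% | 7.32% |
| One contrast, approximate | 5.21% | 4.43% | 4.24% | 4.44% | 5.31% |
| One contrast, exact | 1.13% | 1.65% | 2.02% | 2.53% | 2.95% |

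**Step 4: with an overall test first.** Pairs are tested at 0.05 only if the overall test is significant.

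- Friedman's test (chi-square p-value), n = 8/12/20/30: continuous 4.0/4.7/4.3/4.0%; ratings 3.8/4.6/4.5/4.3%; ranks 4.4/5.5/5.3/5.2%. The simulation error is √(0.05 × 0.95 / 6000) = 0.3 points.
- Exact multinomial test, then exact binomial tests for pairs (single choice), n = 8/10/12/20/30: 3.34/2.24/4.85/3.76/4.78%.

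**The case against.** A reader might infer that Aim 10 runs at a false-positive rate of 12% or more. The documents do not support that. They do not say that all three pairs will be tested, and the plural in the t-test sentence is no evidence: the same wording appears in every section of the SAP, including Aim 3, which has one contrast. What the documents show is an unspecified contrast. The error rate follows only from what the analyst then does.

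A reader might also infer that the plan applies a t-test to nominal data. That is not shown either. Planned paired tests suggest a numeric value per mode, and the single-choice figures rest on a coding that the plan never mentions. What stands is that the format is undefined, and that a single choice would not fit the rule.

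Three further points have weight. The contrast with Aim 3 should not be pressed, because the remaining SAP sections refer only to interventions in general; Aim 10 differs mainly in having three conditions. The questionnaires after the first two modes are not shown to measure preference, which the SAP places after all modes, so they are weak evidence for a score per mode. And multiplicity control for a secondary preference item in iterative device development is open to debate. That last point lowers the weight of the concern, but it does not remove the need to say which modes are compared.

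**Conclusion.** The omission is certain from the text: three modes, tests for two conditions, one 0.05 level, and no contrast, three-mode test, multiplicity rule or response format. Its consequence is conditional. With one contrast named in advance, the error stays near or below 5%. With all three pairs tested two-sided and unadjusted, at an assumed n of 8 to 30, it is about 11%-14% for scores, ratings or ranks with the approximate signed-rank test, and lower with exact tests on coarse data. For a single choice, under the assumed coding, it is 9.3%-12.7% approximate or 3.3%-7.3% exact.

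Preference is labelled secondary, so no primary conclusion changes. It is, however, the only Aim 10 outcome for which the SAP gives an analysis. This is a cheap improvement that should be made, not a flaw that undermines the study.

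**What to change.** State the preference item, when it is asked and its response format, and replace the Aim 10 testing rule with the branch that fits.

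- **Score or rank per mode:** Friedman's test, or a mixed model with mode as a three-level factor. Test pairs at 0.05 only if the overall test is significant. With three modes this is a closed procedure, because equality in any two pairs implies equality in the third. Simulated familywise error with Friedman's test is about 4%-6%. Alternatively, name one contrast in advance and test only that.
- **Single choice:** report the count choosing each mode with exact confidence intervals; use an exact multinomial test of equal preference; then exact binomial tests for pairs under the same gate (familywise error 2.2%-4.9%). Drop Shapiro-Wilk.

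The cost is SAP wording, with no new data or visits. Pairwise claims become somewhat harder to reach. The SAP mixes past and future tense for this outcome, so the documents do not settle whether preference data already exist. If they have been seen, the revised analysis should be labelled post hoc.
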